**Outcomes of Epidural versus Combined Spinal and Epidural (CSE) Anesthetic
Technique on the Success of Trial of Labor after Cesarean (TOLAC): A pilot study**

NCT02105558

Version Date: 03/24/2014

Department of Anesthesiology

Scholarly Research Project Submission Form

Name(s): [name] (PI), [name], FRCA (co PI)

Faculty Mentor: [name], FRCA

Category of Research: Prospective randomized clinical pilot study

Expected length of time for Project: One year or until 60 patients have been enrolled

Title of Research Project: Outcomes of Epidural versus Combined Spinal and Epidural (CSE) Anesthetic Technique on the Success of Trial of Labor after Cesarean (TOLAC): A pilot study

Summary of Project: To compare the effects of epidural versus CSE anesthesia on the success of TOLAC. This will be a prospective clinical study randomizing 60 eligible women into either an epidural group or CSE group. The effects of the specific regional anesthetic on patient's individual labor efforts will then be closely monitored. Written informed consent shall be obtained to enroll the patients in either group. Pain scores and electronic medical record information will be used with non-identifiable coding to determine the resulting outcomes.

Background:

Though it has been said, "once a cesarean, always a cesarean," the current medical stance has changed and now encourages VBAC in a select population of patients. VBAC has several advantages over a repeat cesarean including decreased recovery period, decreased risk of infection, avoidance of major abdominal surgery, and lessened blood loss (1). Predictors for success of VBAC include previous spontaneous vaginal birth, singleton pregnancy, and previous low transverse scar for C-section delivery (1). TOLAC is a reasonable option for select pregnant women and is associated with a 74% likelihood of VBAC (3). Risk factors for failure of VBAC include labor dystocia, advanced maternal age, maternal obesity, fetal macrosomia, GA>40 weeks, short inter pregnancy interval, and preeclampsia (1).

While success of VBAC is associated with fewer complications, failure of VBAC may be associated with increased complications (1). A major concern for VBAC is the possibility for uterine rupture, which may result in hysterectomy and intrapartum fetal hypoxia/death. According to the ACOG guidelines, effective regional analgesia should not be expected to mask the signs and symptoms of uterine rupture, particularly because the most common sign of rupture is fetal heart tracing abnormalities. Adequate

pain relief achieved with either CSE or epidurals may even encourage more women to opt for VBAC. The decision to proceed with TOLAC should occur only after appropriate discussion of the risks and benefits has occurred between the patient and her obstetrician and as long as no other contraindications exist. The final decision should be left up to the patient. There is no reliable way to predict risk of uterine rupture, but it may be associated with classical and low vertical uterine scars, induction of labor, and increased number of prior cesarean deliveries and risk may be decreased by previous vaginal birth (3). Other aspects of VBAC versus repeat cesarean pertaining to the fetus to consider include respiratory function, mother-infant contact, and initiation of breastfeeding, which may be delayed in cesarean deliveries (3).

There is very little research concerning the effects of CSEs and epidurals on women undergoing TOLAC. There have been multiple studies comparing CSE and epidurals on nulliparous and multiparous women, but none have been done specifically on patients undergoing TOLAC. There is only one study comparing CSEs and epidurals in the general population demonstrating similar rates of hypotension and hemodynamic responses in 80 patients undergoing total knee replacement (8). According to the ASA practice guidelines for obstetric anesthesia "nonrandomized comparative studies suggest that epidural analgesia may be used in a trial of labor for previous cesarean delivery patients without adversely affecting the incidence of vaginal delivery. Randomized comparison of epidural versus other anesthetic techniques were not found." They agree that neuraxial techniques improve the likelihood of vaginal delivery for patients attempting VBAC and suggest neuraxial catheter be placed in event of operative delivery (9). Because no study to date has compared CSEs and epidurals and their effects on the success of VBAC, we would like to further investigate this arena.

Inclusion criteria: (all patients meeting ACOG guidelines for TOLAC) ASA II Patients 18 years of age or more with at least one previous elective cesarean delivery, <40 weeks gestational age (GA), vertex singleton pregnancy with use of continuous fetal monitoring.

Exclusion criteria: Patients undergoing TOLAC but refusing regional anesthetic or with contraindication for regional anesthesia, less than 18 years of age, BMI >40 or with associated comorbidities such as gestational diabetes, preeclampsia, abnormal placenta, etc.

Specific outcomes to be looked at include:

Primary outcome:

- Success of vaginal birth after cesarean (VBAC)

Secondary outcomes:

- Success of analgesia/ maternal satisfaction (self- rated pain score of 1-10 prior to, 30 minutes after the regional anesthetic is performed and 24 hrs post-delivery)
- If requiring a repeat C-section or instrumental delivery the success of regional anesthesia for the procedure. (self- rated pain score of 1-10 and necessity to use additional IV pain medication or conversion to general/ spinal anesthesia)
- Immediate side effects: fetal bradycardia, nausea, vomiting, pruritus, hypotension requiring vasopressors
- Late side effects i.e. post dural puncture headache

Methods:

When the patient on the obstetric service requests an epidural for labor analgesia, a consult is immediately placed to the Anesthesia service. Patients who request neuraxial anesthesia for labor analgesia will then be screened for the study. Written informed consent shall be obtained from the patient prior to enrollment in this prospective randomized clinical study. The regional anesthetics will be placed by the obstetrical anesthesia team at Lyndon B. Johnson Hospital, a well-established partner of the University of Texas Medical School at Houston and a facility capable of performing an emergent C-section if necessary. Patients shall be randomized via computer generated randomization sequence and assigned a separate study number different from their medical record number. The study code and MRN will be saved on a linking log on a password protected drive. Standard ASA monitors will be applied to all patients including NIBP, pulse oximetry and fetal heart monitors. Patients will be bolused with 1 liter of LR prior to the procedure via intravenous catheters. In the epidural group, epidurals will be placed in a sterile fashion using a 17g Tuohy needle to locate the epidural space via loss-of-resistance to saline at the lumbar vertebral level. 3 ml of 1.5% lidocaine with 5ug/ml of epinephrine will then be used for test dose to exclude intrathecal or intravenous placement of the catheter. Epidural solution composed of 5ml of 0.2% ropivacaine and another 5 ml of 0.2% ropivacaine will then be administered. In the CSE arm, the epidural space will again be located with a 17g Tuohy needle and dural puncture performed with 25g Pencan needle via needle-through-needle technique. Spinal injection of 2ml 0.2% ropivacaine will then be performed and spinal needle removed. An epidural catheter will then be placed and test dose performed with 3 ml of 1.5% lidocaine with 5ug/ml of epinephrine. Maintenance dose will be via an epidural pump using 0.2% ropivacaine at a rate of 12 ml/hr. Self-determined numeric pain scores will be obtained prior to and after placement of the regional anesthetic and after delivery by nursing staff. Analgesia will be considered successful if the numerical pain score value is 3 or less.

Data collection will be performed via pain scores obtained prior to and following placement of the regional anesthetic and establishment of analgesia, along with data on maternal satisfaction. Electronic medical records will also be used to gather the resulting outcomes.

Data to be collected:

Demographics:

- age
- weight
- height
- ethnicity
- gestational age
- reason for previous cesarean/incision type if known
- previous SVD
- pregnancy number
- cervical dilation at/near time of block (performed by obstetrician)
- estimated fetal weight

Pain scores:

- before RA
- 15 minutes, 30 minutes, and 60 minutes after RA
- 24 hours after delivery

Supplementation of catheter boluses for pain relief and total doses given

Side effects of RA:

- pruritus
- nausea
- vomiting
- hypotension
- post dural puncture headache

Neonatal outcome:

- fetal heart rate immediate post regional
- APGARs at 1 min and 5 min

- birth weight

Delivery:

- date and time at which cervix becomes fully dilated (performed by obstetrician)
- date and time at which the following occur:
 - SVD
 - c-section
 - instrumentation

Maternal Satisfaction

- pain relief
- childbirth experience

Data Analysis Plan:

Power Analysis

Our null hypothesis is that there is no difference in success of VBAC between epidurals and CSEs for women undergoing TOLAC. Our alternative hypothesis is that CSE will result in more successful VBAC than will epidurals. The success rate of VBAC is around 74%. Based on the literature, we expect the success rate with CSE to increase by 20-25%; therefore, given our sample size of 60, we will have 80% power to detect a difference between the two groups.

Primary Outcome

The primary outcome, success for VBAC, will be assessed using χ^2 or the Fisher Exact test, in case of cell sizes <5, to determine if the difference in success rates between the two analgesia groups, CSE and epidural, is statistically significant. Logistic regression analysis will be used to adjust for potential confounders and other factors associated with success or failure of VBAC.

Secondary Outcomes

The secondary outcome, success of analgesia, as measured by pain score on a scale of 1 to 10, will be assessed using ANOVA. Difference in mean pain score between the two groups will be determined in a model with the continuous/count variable pain score as the dependent variable and analgesia group as the independent variable.

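### No blocking or stratification by previous vaginal birth is described and the test of significance is unadjusted; stratifying the allocation and the primary analysis by it is a cheap improvement

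*Combined protocol and SAP*

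**What the plan says.** All references are to the combined protocol and SAP.

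- **Methods.** The only description of allocation is "Patients shall be randomized via computer generated randomization sequence". The Summary of Project adds "randomizing 60 eligible women into either an epidural group or CSE group". Neither gives a ratio, block size or stratification factor.
- **Background.** "Predictors for success of VBAC include previous spontaneous vaginal birth, singleton pregnancy, and previous low transverse scar for C-section delivery".
- **Eligibility.** Singleton pregnancy is required. Scar type is partly settled by being a TOLAC candidate. A previous vaginal birth is neither required nor excluded, so it varies between women.
- **Data to be collected, Demographics.** Previous SVD is one of ten baseline items. It is history, so it is known before allocation.
- **Data Analysis Plan, Primary Outcome.** Success of VBAC "will be assessed using χ^2 or the Fisher Exact test, in case of cell sizes <5", and this is the test tied to statistical significance. The next sentence reads "Logistic regression analysis will be used to adjust for potential confounders and other factors associated with success or failure of VBAC". It names no covariates and does not say whether the regression or the simple test decides the conclusion.
- **Data Analysis Plan, Power Analysis.** "The success rate of VBAC is around 74" per cent; "we expect the success rate with CSE to increase by 20-25" per cent; "given our sample size of 60, we will have 80% power to detect a difference between the two groups".

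**The concern.** Of the three predictors of success that the plan names, previous vaginal birth is the one clearly left free to differ between the arms. With 60 women, a visible difference in its share is quite possible. The unadjusted comparison would then carry part of that difference as apparent benefit or harm of CSE. The regression could separate the two, but as written it can be fitted in many ways after the data are seen, and nothing says how a disagreement with the chi-square or Fisher result would be settled. What is at stake is some precision and how readily a single small result can be interpreted.

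**Working it through.** **Inputs.** From the plan: 60 women, 74% success with epidural, an increase of 20-25%. Not in the plan and assumed here: 1:1 allocation (30 per arm), alpha 0.05 two-sided, prevalence of previous vaginal birth 30-50%, and success 20-30 points higher in those women with 74% overall.

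**1. The plan's own power figure.** Normal approximation, pooled variance under the null, absolute reading of the increase.
- 74% v 94%: null SE = √(2 × 0.84 × 0.16 / 30) = 0.0947; alternative SE = √((0.1924 + 0.0564) / 30) = 0.0911; z = (0.20 − 1.96 × 0.0947) / 0.0911 = 0.16; power 56%.
- 74% v 99%: null SE 0.0882, alternative SE 0.0821; z = (0.25 − 1.96 × 0.0882) / 0.0821 = 0.94; power 83%.

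The stated 80% is met only near the top of the effect range. At 20 points there is little precision to spare.

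**2. Failures available to the regression.** Under the null, 60 × 0.26 = 15.6. At 74% v 94%, 30 × 0.26 + 30 × 0.06 = 9.6 (8.1 at 74% v 99%). That supports one or two covariates, not ten baseline items.

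**3. Size and likelihood of an imbalance.** The numbers with a previous vaginal birth are taken as independent Binomial(30, prevalence) in each arm. A 20-point imbalance is a difference of 6 women or more. Shift in the unadjusted difference = mean imbalance × predictor effect.

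| Prevalence | Chance of ≥20 points, either direction | Favouring CSE | Mean imbalance when it occurs | Shift, 20-point effect | Shift, 30-point effect |
|---|---|---|---|---|---|
| 30% | 12.0% | 6.0% | 23.5 points | 4.7 points | 7.1 points |
| 40% | 14.7% | 7.3% | 24.0 points | 4.8 points | 7.2 points |
| 50% | 15.5% | 7.8% | 24.2 points | 4.8 points | 7.3 points |

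The shift compares with a null SE of √(0.1924 × 2 / 30) = 11.3 points.

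**4. Error rates.** Simulation, 300,000 trials per setting over the assumed grid, chi-square without the Fisher fallback. Averaged over randomisations, two-sided type I error of the unadjusted test is 4.9-5.0%. Given one particular imbalance (15 v 9 women at 40% prevalence, effect 20-25 points), it is 5.8-6.2%, with 4.9-5.6% falling in favour of CSE. With balanced arms, 2.0-2.2% falls in favour of CSE.

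**5. What stratifying gains.** With prevalence π, predictor effect g and balanced strata, the SD of the difference is √((0.1924 − π(1 − π)g²) / 15).
- π = 0.3, g = 0.2: √(0.1840 / 15) = 11.1 points.
- π = 0.4, g = 0.3: √(0.1708 / 15) = 10.7 points.
- π = 0.5, g = 0.3: √(0.1699 / 15) = 10.6 points; 10.7 in simulation, because an odd number in a stratum leaves one woman unbalanced.

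Power was simulated at a treatment odds ratio of 5.5, since (0.94/0.06) / (0.74/0.26) = 5.5. Unstratified and unadjusted it is 55-58%. Stratified with a Cochran-Mantel-Haenszel test it is 58-59%. The gain is about 1-2 points over most of the grid and 2.7 at its strongest corner (50% prevalence, 30-point effect).

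**6. Stratifying but keeping the unadjusted test.** Type I error falls to 3.7-4.5%. The Cochran-Mantel-Haenszel test after stratification holds 4.9-5.0%. The analysis therefore has to follow the design.

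**The case against.** A reader might infer that the sequence is known to be simple, or that an imbalance would pass unchecked into the conclusion and bias the trial. The documents support neither.

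- **Silence is not a statement.** The Methods neither state nor exclude blocks or strata. The accurate wording is that none is described.
- **An adjusted analysis is planned.** The regression sits under the same Primary Outcome heading, and previous SVD is an obvious candidate covariate. Adjusting for one binary factor is far less demanding than a multi-covariate model. What remains is that neither the covariates nor the standing of the regression is fixed.
- **Randomisation already controls the error rate.** The higher false-positive rate for CSE applies only after an unlucky draw. The opposite draw lowers it, and the average is about nominal. A 5-7 point shift also lies within one standard error.
- **The choice of factor is a judgement.** The Background also lists maternal age and obesity among the risk factors for failure, and both can vary within the eligibility limits. A 60-woman pilot at one hospital may reasonably randomise simply and adjust later.
- **Unequal arm sizes matter little.** If allocation is simple, a 36/24 or worse split has a probability of 2 × P(Bin(60, 0.5) ≤ 24) = 15.5%, but the standard error rises only from 11.3 to √(0.1924 × (1/36 + 1/24)) = 11.6 points.

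Most of this stands. It keeps the point to an optional improvement but does not remove it: the factor is named in the plan, already collected and known before allocation, and the test tied to significance ignores it.

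**Conclusion.** The point holds as a cheap improvement and not as an error that invalidates the design. No stratification is described, the significance test is unadjusted, and the planned regression lacks a covariate list and a stated rank. Under the assumed 30-50% prevalence and 20-30 point effect, a 20-point or larger imbalance has a 12-16% chance (6-8% favouring CSE), and one favouring CSE shifts the unadjusted difference by about 5-7 points. There is no average bias and no inflation of the overall type I error. The benefit of acting is an SD of about 10.7-11.1 in place of 11.3 points, about 1-2 points of power, and a result that is easier to read if the arms differ. Prevalence and predictor effect are not in the documents. With a weaker predictor, the shift and the gain shrink in step.

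**What to change.** 1. In the Methods, state 1:1 allocation in permuted blocks of varying size, stratified by previous vaginal birth (yes/no). If the sequence is already blocked or stratified, say how.
2. In the Primary Outcome section, make the analysis stratified by that factor primary: the Cochran-Mantel-Haenszel test with the Mantel-Haenszel risk difference. Keep the unadjusted chi-square or Fisher test as supportive. Presenting the stratified result only alongside an unadjusted primary test would leave the deciding test conservative.
3. If the logistic regression stays, label it secondary, prespecify previous vaginal birth as a covariate, and limit the list to one or two.

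Cost: a second allocation list, slightly more set-up, and a few lines of text. Two strata at one site are workable with 60 women, and varying the block size limits predictability. No new data are needed.

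### The plan describes no masking of the woman, the nurses who collect pain scores, the obstetric team or the person taking outcomes from the record, although partial masking looks feasible at low cost

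*Combined protocol and SAP*

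**What the plan says.** **Endpoints.** The primary outcome is listed as "Success of vaginal birth after cesarean (VBAC" (the abbreviation's bracket closes there), with no criteria for classifying failure and no statement of who decides on a repeat cesarean. Pain is self-rated: "Self-determined numeric pain scores will be obtained prior to and after placement of the regional anesthetic and after delivery by nursing staff" (Methods). Maternal satisfaction with pain relief and with the childbirth experience is listed under Data to be collected, with no collector named. Delivery outcomes come from the electronic medical record.

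**Roles.** "The regional anesthetics will be placed by the obstetrical anesthesia team" (Methods). The obstetrician is named for cervical assessments, for example "date and time at which cervix becomes fully dilated (performed by obstetrician" (Data to be collected, Delivery).

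**Expectation.** "Our alternative hypothesis is that CSE will result in more successful VBAC than will epidurals" (Data Analysis Plan, Power Analysis).

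**Allocation and coding.** "Patients shall be randomized via computer generated randomization sequence and assigned a separate study number different from their medical record number" (Methods), with study code and record number held in a protected log. "Pain scores and electronic medical record information will be used with non-identifiable coding to determine the resulting outcomes" (Summary of Project). The text is silent on masking, masked assessment, masked abstraction and open-label status.

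**The concern.** Randomization balances the arms at entry. It does not protect an outcome that someone rates, or partly decides, afterwards while knowing the arm. The woman rates her own pain and satisfaction. A nurse who knows the technique may elicit a score differently. The course of labor that ends in repeat cesarean may be read differently by someone who expects one technique to help. The plan states such an expectation, so influence on these outcomes would tend to favor CSE.

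The planned logistic regression adjusts for potential confounders and other factors associated with VBAC success. It cannot remove a difference created by knowledge of the arm, so masking has to be settled before enrollment.

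**Working it through.** **1. Does any provision amount to masking?** The nearest candidates are the study number, the linking log and the non-identifiable coding. The first two separate a woman's identity from her study data, and the third does the same in reporting outcomes. None hides the technique from anyone who treats her, questions her or reads her record. Answer: no.

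**2. Who could be kept unaware?** The two arms as the Methods describe them:

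| Step | Epidural arm | CSE arm |
|---|---|---|
| Placed by | obstetrical anesthesia team | same |
| Needle to epidural space | 17g Tuohy | 17g Tuohy |
| Dural puncture | none | 25g needle through the Tuohy |
| Initial ropivacaine 0.2% | 5 ml + 5 ml, epidural | 2 ml, spinal |
| Catheter | yes, implied by a test dose that "will then be used for test dose to exclude intrathecal or intravenous placement of the catheter" | yes, stated |
| Test dose | 3 ml lidocaine 1.5% with epinephrine | same |
| Maintenance | epidural pump, 12 ml/hr | one sentence that reads as common to both |

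The arms differ during placement and in initial dosing. After that, as described, the set-up is the same. Those placing the block cannot be masked. The others can be left untold, with some risk that they find out.

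**3. How much could it matter for the primary outcome?** The plan gives no figure for bias, so there is none to reproduce. This is an illustration.

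Inputs: 74% success (Power Analysis); 60 women in total; equal allocation, hence 30 per arm (assumed, since the ratio is not stated); two-sided 5% level (assumed); no true effect; a shift d in the observed CSE success rate caused by knowledge of the arm (assumed).

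Formula: rejection rate = sum over all a, b from 0 to 30 of Bin(a; 30, 0.74 + d) × Bin(b; 30, 0.74), counting only tables (a successes of 30 with CSE, b of 30 with epidural) whose p-value is at most 0.05.

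| Assumed shift d | Women (30 × d) | Fisher exact | Chi-square, uncorrected |
|---|---|---|---|
| 0 | 0 | 2.6% | 4.9% |
| 5 points | 1.5 | 3.9% | 7.2% |
| 10 points | 3 | 9.2% | 15.3% |
| 15 points | 4.5 | 20.8% | 32.0% |
| 20 points | 6 | 42.1% | 59.8% |

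The plan uses chi-square, or Fisher when cells are below 5. At 30 per arm every table that Fisher rejects is also rejected by uncorrected chi-square, so the plan's mixed rule lies between the two columns.

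**4. Sensitivity to one delivery.** Against 22/30 with epidural, 28/30 with CSE gives Fisher p = 0.080 and 29/30 gives p = 0.026. Any discrete test at this size behaves this way, masked or not, so this shows fragility and is not evidence of bias.

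No calculation was made for pain or satisfaction: the documents give no standard deviation or expected difference.

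**The case against.** The strongest reply is that delivery mode is an objective event recorded with date and time, that this is a 60-woman pilot, and that masking is weakest where it is most wanted. The woman is the pain rater and undergoes different initial steps. Scores at 15, 30 and 60 minutes fall when speed of onset may reveal the arm. The nurse may have seen the procedure, and the record itself may show the technique. All of this stands as a limit on what masking can achieve. It does not explain why the plan leaves the matter unstated. Nor does the pilot label, since the plan claims 80% power and tests for significance.

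A reader might also infer four stronger things that the documents do not support:

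- **That the primary endpoint rests on an obstetrician's decision.** The text never assigns the decision on repeat cesarean. Its Background gives the patient the final say on attempting labor, and the obstetrician is tied only to cervical assessments. That judgment enters is a reasonable clinical inference, no more.
- **That nurses collect the satisfaction items.** Only the pain scores are assigned to nursing staff.
- **That masking costs almost nothing.** The documents say nothing on cost, and masking could only be partial.
- **That a small shift could manufacture the result.** A 5-point shift gives 3.9% by Fisher, still below 5%, and 7.2% by uncorrected chi-square. Marked inflation needs larger shifts, and nothing in the documents indicates their size.

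**Conclusion.** The gap is real: no role is described as masked, and the identity coding does not do that job. Pain and satisfaction are the most exposed outcomes because they are subjective. The primary outcome is exposed to the extent that judgment affects the route to repeat cesarean. Under the stated assumptions (30 per arm, two-sided 5% level, no true effect, 74% in the epidural arm), an assumed 10-point shift raises the Fisher rejection rate from 2.6% to 9.2%, and a 15-point shift raises it to 20.8%. These figures show what knowledge of the arm could do. They are not a finding that the trial will be biased. The point rests on the protocol text supplied, from which consent pages were removed. It is a cheap improvement to the plan and does not by itself undermine the design.

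**What to change.** Add to Methods:

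- The woman is not told which technique she was assigned.
- Where existing staffing allows, pain scores (in particular the 24-hour score) and satisfaction are recorded by a nurse who has not been told the technique.
- Delivery outcome is taken from the record by an existing team member who does not have the allocation.
- The obstetric team is not routinely told the study arm for research purposes. Clinical records, handover and disclosure for care are not restricted in any way.
- Known unmasking is logged.
- Those placing the block are unmasked, and the remaining lack of masking is reported as a limitation.

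Consent wording should match. No criterion for cesarean is proposed here; that is a clinical matter for the investigators.

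**Cost.** Protocol and consent wording and a short instruction to existing staff, with no added patients and no change of treatment. The documents do not show how staffing is arranged, hence the condition on the nurse. **Downside.** Masking is partial: the nurse may see the procedure, onset speed may reveal the arm, and an abstractor may meet the technique in the record.

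### Supplementary boluses are recorded but enter no planned analysis, and pain scores taken after a bolus count at face value in the analgesia comparison

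*Combined protocol and SAP*

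**What the plan says.** The protocol treats labor analgesia in four places.

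- **Secondary outcomes list.** Success of analgesia, listed together with maternal satisfaction, rests on a "self- rated pain score of 1-10 prior to, 30 minutes after the regional anesthetic is performed and 24 hrs post-delivery". Rescue is not mentioned.
- **Methods.** The success rule is "Analgesia will be considered successful if the numerical pain score value is 3 or less". It sets no condition on supplementation and names no time point.
- **Data to be collected.** Pain scores are taken before the block, at "15 minutes, 30 minutes, and 60 minutes after RA", and 24 hours after delivery. A separate line records "Supplementation of catheter boluses for pain relief and total doses given".
- **Data Analysis Plan, Secondary Outcomes.** "The secondary outcome, success of analgesia, as measured by pain score on a scale of 1 to 10, will be assessed using ANOVA". The model has "pain score as the dependent variable and analgesia group as the independent variable". There is no term for boluses and no rule for a score that follows one.

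The categorical outcomes named for chi-square or Fisher testing are the success of regional anesthesia at operative delivery and the side effects. The logistic regression under Primary Outcome concerns VBAC and names no bolus variable.

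**The concern.** A woman whose block is inadequate at 15 minutes, who is given a bolus and then scores 2 at 30 minutes, counts as a success of her assigned technique. Her score of 2 also enters her group's mean. Nothing in the plan marks her out from a woman who scored 2 on the initial block alone.

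The plan expects such boluses, since it has a line for them. Initial dosing also differs between the arms: in the Methods the epidural arm is given ropivacaine through the catheter after the test dose, while the CSE arm is given a spinal dose and then a catheter with a test dose. Unequal need for rescue is therefore plausible, although the documents do not show it.

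The plan already counts extra medication in a neighboring outcome. For C-section or instrumental delivery, success is judged by the pain score together with the need for additional IV medication or conversion. Labor analgesia has no equivalent.

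At stake is the reading of the first-listed secondary outcome. The trial could report similar pain scores and leave unreported that one technique needed more supplementation to reach them.

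**Working it through.** The documents state no rate, standard deviation or power for analgesic success or rescue, so there is no figure to reproduce. The omission is established by reading the outcome list, data list and analysis plan together. The arithmetic below only shows how rescue acts on the comparison.

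**Inputs**
- From the documents: success is a score of 3 or less; the listed outcome time after the block is 30 minutes; 60 women in total.
- Assumed: 30 per arm (the ratio is not stated); share *b* scoring 3 or less without rescue, 70% in one arm and 90% in the other; share *r* of the remaining women brought to 3 or less by a bolus before the score; mean score 2 among women at 3 or less, and 6 among the others.

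**Success proportion.** Observed success = b + (1 − b)r. With the same r in both arms, the observed difference is (1 − r) times the rescue-free difference.

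**Mean score, as in the planned ANOVA.** Mean = 2 + 4(1 − b)(1 − r). The difference in means is 4 × 0.20 × (1 − r) = 0.8(1 − r).

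| r, both arms | Observed success | Difference | Approximate power | Difference in mean score |
|---|---|---|---|---|
| 0 | 70% v 90% | 20 points | 49% | 0.80 |
| 0.5 | 85% v 95% | 10 points | 25% | 0.40 |
| 0.8 | 94% v 98% | 4 points | 12% | 0.16 |
| 1 | 100% v 100% | 0 | – | 0 |

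Power is the normal approximation for two proportions, 30 per arm, two-sided 0.05. For r = 0 the standard error is √(2 × 0.8 × 0.2/30) = 0.103 under the null and √((0.21 + 0.09)/30) = 0.100 under the alternative. This gives Φ((0.20 − 1.96 × 0.103)/0.100), or about 49%.

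**Other starting rates, same r in both arms.** At r = 0.5 and 0.8, 60% v 90% shrinks from 30 points to 15 and 6, and 80% v 90% shrinks from 10 points to 5 and 2.

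**Rescue in the lower arm only.** With 70% v 90%:
- r = 0.5 gives 0.70 + 0.30 × 0.5 = 85% v 90%, so 5 points remain.
- r = 0.8 gives 0.70 + 0.30 × 0.8 = 94% v 90%, so the order reverses.
- Reversal needs 0.70 + 0.30r > 0.90, that is r > 0.20/0.30 = 67%. For 65% v 85% it needs r > 0.20/0.35 = 57%.

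Boluses given after the 60-minute score cannot change any of the three post-block scores. For the 30-minute outcome, only boluses given and effective before that time matter.

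**The case against.** The strongest reply is that pain under each technique, with supplementation as needed, is a legitimate treatment-policy question. Both arms have a catheter, and a rescued score is a true score. That stands. It means the score-only result should stay, and that the gap lies in not saying which question is asked and in leaving bolus use out of the report.

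Second, the 3-or-less rule has no test of its own, because the plan compares mean scores by ANOVA. That is correct, so a case resting on success proportions alone would miss the planned analysis. The last column of the table shows that the means shrink by the same factor.

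Third, the categorical list is worded openly and could admit a bolus comparison. It could, but one chosen after the data are seen is not a planned one.

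A reader might also infer three stronger things that the documents do not support.
- *That the bolus record is the only measure of analgesia after 60 minutes.* It is not. Operative deliveries have their own pain score, and satisfaction with pain relief is collected. What is true is that no routine score is listed for all women between 60 minutes and 24 hours after delivery.
- *That the comparison will be reversed.* In the illustrations this needs effective early rescue of more than 57% to 67% of the remaining women, in one arm only.
- *That masking will be substantial.* It depends on boluses before the 30-minute score, and the documents give neither their frequency nor their timing.

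Finally, a rescue-free endpoint depends on the decision to bolus, and the documents describe no blinding. That also stands, and is why it belongs beside the score-only result and not in its place.

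**Conclusion.** The point holds as an omission: labor analgesia is judged without regard to prior boluses, and the recorded boluses and total doses are used in no planned analysis. Its direction is clear if boluses precede the 30-minute score: equal rescue shrinks the contrast by the factor (1 − r), and unequal rescue shifts it. Its size in this trial is unknown, and every rate above is an assumption. The 24-hour post-delivery score is less exposed. The matter concerns a secondary outcome of a pilot, and VBAC success is unaffected. It is a cheap improvement, not a fault that undermines the trial.

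**What to change.** 1. **Secondary Outcomes, from data already listed.** Compare between arms the proportion of women with any supplementary bolus (chi-square or Fisher) and the total supplementary dose. Define supplementary as doses beyond the initial dosing and infusion written in the Methods; otherwise the arms differ by design.
2. **Data to be collected.** Add the clock time of each bolus to the existing line, so that boluses can be placed before or after the 30-minute score.
3. **Secondary Outcomes, with that time field.** Report success at 30 minutes defined as a score of 3 or less with no prior supplementary bolus, tested by chi-square or Fisher. Show it beside the score-only result and the ANOVA.

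The cost is one time field and two or three further secondary comparisons in a 60-woman pilot. Stated success rates will be lower on the rescue-free definition, and that endpoint carries the dependence on an apparently unblinded decision to bolus. The time field should be settled before data collection, because scores taken after a bolus may not be separable later. No change to dosing or to who receives rescue is proposed.
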